5.3 General Concomitant Medication and Supportive Care Guidelines

Patients may receive non-chemotherapeutic agents for premedication and supportive care as per the standard of care while on study.

5.4 Duration of Therapy

In the absence of treatment delays due to adverse events, radiotherapy should be completed within 1 month of the first day of radiotherapy (Day 28 of protocol treatment). Patients may receive systemic therapy off-protocol no earlier than 4 weeks after starting SBRT.

5.5 Duration of Follow Up

Patients will be followed for 1 year after beginning radiotherapy. Patients removed from study for unacceptable adverse events will be followed until resolution or stabilization of the adverse event.

5.6 Criteria for Removal from Study

Patients will be removed from study when one of the following criteria applies:

- Intercurrent illness that prevents administration of SBRT,
- Unacceptable adverse event(s),
- Death,
- Patient decides to withdraw from the study, or
- General or specific changes in the patient's condition render the patient unacceptable for further treatment in the judgment of the investigator/treating physician.

The reason for study removal and the date the patient was removed must be documented in the Case Report Form.

6. RADIATION THERAPY

6.1 Simulation

6.1.1 SBRT

6.1.1.1 Patient Positioning

Patients must be simulated in a stable, supine position capable for reproducibility of positioning at the time of treatment, to allow for the patient to feel as comfortable as possible. A prone position is not allowed. A variety of immobilization systems may be utilized with reference to the treatment delivery coordinate system.

6.1.1.2 Simulation

CT simulation will be performed with proper patient positioning and immobilization. CT will be the primary image platform for treatment planning. The use of intravenous contrast is recommended if it can help delineate the tumor or normal tissues (e.g. for liver metastases). Additionally, oral, rectal, or bladder contrast are recommended if these agents will improve tumor or target delineation.

When available, 4D CT should be used for all sites where there is concern for movement due to normal respiration.

6.2 Premedications

No premedications are required for any aspect of radiotherapy, however corticosteroid, anti-emetic, anti-anxiety, and narcotic/non-narcotic pain medications are allowed per physician discretion.

6.3 Target Volumes

When available, imaging studies such as MRI and PET are may be fused with planning CT to aid contouring of the target volumes.

6.3.1 Target Definition

6.3.1.1 The definition of volumes will be in accordance with the ICRU Report 62: Prescribing, Recording and Reporting Photon Beam Therapy. [65]

6.3.1.2 A gross tumor volume (GTV) will be entered for each lesion, based on available imaging data.

6.3.1.3 In the absence of respiratory gating, for any lesion that is subject to movement from respiration, an internal target volume (ITV) will be defined as the volume that accounts for intrafraction target motion.

6.3.1.4 A clinical target volume (CTV) will be defined as the GTV or ITV (when available) plus a margin for microscopic extension.

6.3.1.5 A planning target volume (PTV) will be determined which will correspond to CTV plus appropriate margin for tumor motion and set-up uncertainty.

6.3.1.6 Separate GTV, CTV, PTV, and if applicable, ITV contours, will be created for all sites of gross disease.

6.4 Treatment Planning

6.4.1 3D coplanar or non-coplanar beam arrangements will be custom designed for each case to deliver highly conformal prescription dose distributions. The treatment plan used for each patient will be based on an analysis of the volumetric dose, including dose volume histogram of the PTV and normal structures. 3D “forward” planning or “inverse” planning with beamlet intensity modulated treatment planning are allowed.

6.4.2 Respiratory gating is strongly recommended if there is significant movement of the GTV with respiration.

6.4.3 Treatment is to be delivered using a linear accelerator and photon energies ≥ 6 MV.

6.4.4 Corrections will be made to account for tissue heterogeneity.

6.4.5 Any dose $> 110\%$ must be within the PTV.

6.5 Dose Specifications

Doses will be prescribed to the PTV. The PTV may be covered by a lower isodose line than usually used in conventional radiotherapy planning, ranging from 60-100%. Ideally, the prescription dose will cover $>90\%$ of the GTV ($V_{100} \text{ GTV} > 90\%$, and $V_{95} \text{ PTV} > 90\%$). Hot spots within the PTV are allowed, unless the PTV also overlaps an organ at risk. A lower coverage goal will be acceptable if necessary to meet normal tissue constraints, which will be assigned priority over tumor coverage.

6.5.1 SBRT

At all dose levels in dose escalation, the preferred SBRT dose is 50 Gy in 5 fractions of 10 Gy to all sites of disease, including the primary tumor if it can not be treated with surgical resection or alternative local therapy. However, normal tissue constraints are of priority in selecting the prescribed dose, and if the dose to normal tissues exceeds the normal tissue dose constraints, then dose can be de-escalated to a lower dose, such as 8 Gy x 5. **One site in which de-escalation is routinely expected includes the treatment of vertebral body metastases, in which the preferred SBRT dose is 27-30 Gy in 3 fractions of 9-10 Gy.**

5.6 Critical Structures

6.6.1 Critical structure dose constraints are per Table 1. These dose constraints are based on NRG BR002, a NRG Oncology cooperative group prospective Phase I clinical trial of SBRT for the treatment of multiple metastases in patients with oligometastatic cancer.

Table 1: Normal tissue critical structure dose constraints

Serial Organ	Volume	Dose (Gy)	Avoidance Endpoint
Spinal Cord	<0.03 cc	28	Myelitis
	<0.35 cc	22	Myelitis
	<1.2 cc	15.6	Myelitis [66]
Ipsilateral Brachial Plexus	< 0.03 cc	32	Brachial Plexopathy (RTOG 0813)
	<3 cc	30	Brachial Plexopathy (RTOG 0813)
Cauda Equina	<0.03 cc	32	Neuritis (AAPM TG-101)
	<5 cc	30	Neuritis (AAPM TG-101)
Sacral Plexus	<0.03 cc	32	Neuropathy (AAPM TG-101)
	<5 cc	30	Neuropathy (AAPM TG-101)
Trachea and Ipsilateral Bronchus (Non-adjacent wall)	<0.03cc	40	Stenosis/Fistula
	<5cc	32	Stenosis/Fistula (RTOG 0813)
Esophagus* (Non-adjacent wall)	<0.03cc	35	Stenosis/Fistula [66]
	<5 cc	27.5	Stenosis/Fistula (RTOG 0813)
Heart/Pericardium	<0.03 cc	38	Pericarditis [66]
	<15 cc	32	Pericarditis (RTOG 0813)
Great vessels (Non-adjacent wall)	<0.03 cc	53	Aneurysm [66]
	<10 cc	47	Aneurysm (RTOG 0813)
Skin	< 0.03cc	38.5	Ulceration
	< 10cc	36.5	Ulceration
Stomach	< 0.5cc	35	Ulceration/Fistula
	< 5cc	26.5	Ulceration/Fistula
Duodenum*	< 0.5 cc	30	Ulceration (RTOG 1112)
	< 5 cc	18.3	Ulceration [67]

Jejunum/ileum*	< 0.03 cc	32	Ulceration
	< 30cc	20	Enteritis/Obstruction
Bowel*	< 0.03 cc	40	Ulceration
	<20 cc	28.5	Colitis/Fistula
Rectum*	<0.03 cc	55	Ulceration
	<3.5 cc	50	Proctitis/Fistula
	<20 cc	32.5	Proctitis/Fistula
Bladder	< 0.03	38	Cystitis/Fistula
	<15 cc	20	Cystitis/Fistula
Ureter	<0.03 cc	45	Stenosis
Penile Bulb	<3 cc	30	Impotence [66]
Femoral head	<10 cc	30	Necrosis
Bile Duct	<0.03 cc	41	Stenosis
Renal hilum/Vascular Trunk	<15 cc	23	Malignant Hypertension
Rib	<0.03 cc	57	Pain or Fracture
	<5 cc	45	Pain or Fracture
Parallel Organ	Volume	Dose (Gy)	Avoidance Endpoint
Lung (total)	< 37% lung volume	13.5	Pneumonitis
	< 1500 cc	12.5	Basic Lung Function (RTOG 0813)
	< 1000 cc	13.5	Pneumonitis (RTOG 0813)
Ipsilateral Kidney	< 130 cc	14.5	Basic Renal Function
Total Kidney	< 200cc	18	Basic Renal Function
Liver	<700 cc	21	Liver Function [66]

*Note: avoid circumferential irradiation.

Dose volume histograms (DVHs) will be constructed to assess dose to PTV and normal tissue structures. The pertinent critical structure dose constraints will be determined by the location of the treated lesion. These must be met prior to plan approval, otherwise target coverage, or prescription dose, must be decreased to meet the constraints as above.

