1.2. Secondary Objectives

- 1.2.1 To determine the toxicity profile of SBRT.
- 1.2.2 To determine the feasibility of delivering 5-fraction SBRT based on proposed normal tissue constraints in a variety of organ sites. (i.e., the ability to treat >80% of enrolled patients according to protocol guidelines).
- 1.2.3 To describe treated lesion control (LeC), progression free survival (PFS), and patterns of failure.
- 1.2.4 To determine the feasibility of accrual and adequacy of eligibility criteria by defining the proportion of eligible cases of metastatic RCC presented at the weekly multidisciplinary genitourinary conference at the University of Chicago Medical Center.
- 1.2.5 To make a preliminary evaluation regarding potential biomarkers in patient serum which may be endpoints in a follow-up study (e.g. genetic or immunologic biomarkers).

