There are numerous SBRT fractionation regimens that have been evaluated [38, 39, 41, 52-54]. However, the optimal dose and number of fractions of SBRT are unknown. A prior phase I dose escalation trial was performed to evaluate SBRT for oligometastatic cancer at the University of Chicago. This study used a modified Fibonacci dose escalation to identify the maximal safe organ-specific doses that could be delivered in a 3-fraction SBRT regimen [45]. However, the patient cohort in this study was heterogeneous, with only 8 of 61 patients (13%) having renal cell malignancies. Additionally, different doses for each specific organ of involvement were used. This approach is more complex and may be more difficult to implement in subsequent trials and in the community. In addition, 5-fraction SBRT may be better tolerated by critical structures, particularly for tumors near gastrointestinal critical structures. For primary tumors, Wersall et al used 40 Gy in 5 fractions for tumors up to 10 cm in size [47]. Videtic et al evaluated the use of a SBRT regimen of 50 Gy in 5 fractions in medically inoperable non-small cell lung cancer and found a 3 year local control rate of 94.4% and acceptable toxicity [41]. In addition, 50 Gy in 5 fractions is the starting dose and fractionation of RTOG 0813, a Phase I/II dose escalation study of SBRT in non-small cell lung cancer currently open in multiple centers. Typically, the dose and fractionation schemas used to treat metastatic lesions in the lung are similar to those used in primary lung cancer. The 50 Gy in 5 fractions schema also has the benefit of being tolerable in multiple organ sites other than the lungs [55]. Thus, 50 Gy in 5 fractions was selected as the preferred schema in our trial, with 40 Gy in 5 fractions used as an alternative dose when normal tissue constraints cannot be met using the preferred dose.

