2.4 Rationale for current study

The above evidence suggests a role for aggressive local treatment of metastatic lesions in RCC. We hypothesize that SBRT can be safely and effectively delivered in patients with oligometastatic RCC. Results will inform the development of a larger, multicentric trial.

This study will evaluate a 5-fraction regimen in patients who have a histology diagnosis of metastatic RCC with 5 or fewer sites of disease. All organs of involvement will receive 5 fractions with a preferred dose of 50 Gy in 5 fractions. This pilot study will evaluate the ideal candidates for this approach, the likely accrual and accrual rate of a phase II study, and the optimal dosimetric and dose/fractionation considerations in pursuing this approach. In addition, this study will allow for the collection of data to possibly refine eligibility and treatment

delivery for future studies, and help determine sample size calculations for the next generation trials. Subsequent testable hypotheses could include randomized comparisons of SBRT +/- concurrent molecularly targeted systemic therapy, observation +/- SBRT, or systemic therapy +/- SBRT.

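### Vertebral plans given in 3 fractions are checked against one dose-limit table with no fraction number; if its totals are for 5 fractions, the cord limits are 29-49% looser in BED than intended

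*Combined protocol and SAP*

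**What the plan says.** Section 6.5.1 sets 50 Gy in 5 fractions as the general schedule and names one routine exception: "the treatment of vertebral body metastases, in which the preferred SBRT dose is 27-30 Gy in 3 fractions of 9-10 Gy".

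Section 6.6.1 (under the heading printed as 5.6 Critical Structures) then states: "Critical structure dose constraints are per Table 1". The table has four columns: organ, volume, dose in Gy, and the endpoint to be avoided. It has no column, title or footnote giving a number of fractions. The rows nearest to a vertebral target are:

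- spinal cord: 28 Gy (<0.03 cc), 22 Gy (<0.35 cc), 15.6 Gy (<1.2 cc);
- cauda equina: 32 Gy (<0.03 cc), 30 Gy (<5 cc).

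On which rows apply, the text says: "The pertinent critical structure dose constraints will be determined by the location of the treated lesion". On their force, it says: "These must be met prior to plan approval"; otherwise coverage or prescription must come down.

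Elsewhere the plan is framed around 5 fractions. Section 2.4: "All organs of involvement will receive 5 fractions with a preferred dose of 50 Gy in 5 fractions". Aim 1.2.2: "To determine the feasibility of delivering 5-fraction SBRT based on proposed normal tissue constraints in a variety of organ sites".

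**The concern.** The effect of a total dose on late-responding tissue depends on how many fractions deliver it. One set of totals therefore cannot give the same protection in 3 fractions and in 5. The protocol uses both schedules, makes the limits a condition of plan approval, and does not let the limit vary with the schedule.

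If the totals were set for 5 fractions, a vertebral plan can meet every row and comply fully, yet give the cord a higher biological dose than the limits were meant to allow. Section 7.1.6 names damage to the cord or cauda equina, with paralysis, as the additional risk of spine treatment. It calls this rare, but the outcome is severe. The issue is the safety of vertebral plans, not the trial's inference.

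**Working it through.** **The plan's own figures.** The documents give no BED figure to reproduce. The one related design figure is the stated 78.8% power of the toxicity rule in section 12.1. An exact binomial recursion over 25 patients with the stated boundaries gives 78.84% at a 20% rate and 5.00% at a 5% rate. That figure is right and does not depend on this point.

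**Inputs.** From the documents: the cord and cauda equina rows of Table 1; 27-30 Gy in 3 fractions (6.5.1); the 110% rule (6.4.5, read as percent of prescription). Assumed, because the documents do not give them: the linear-quadratic model; alpha/beta of 2-4 Gy for cord and nerve, with 10 Gy as an extreme; Table 1 read as 5-fraction totals.

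**Formula.** For total dose D in n fractions, BED = D × (1 + (D/n)/(alpha/beta)).

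**Example.** Cord 28 Gy, alpha/beta 2:
- 5 fractions: 28 × (1 + 5.6/2) = 106.4
- 3 fractions: 28 × (1 + 9.333/2) = 158.7
- ratio 158.7/106.4 = 1.491

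**Cord rows: BED in 3 fractions divided by BED in 5, same total.**

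| Row | a/b 2 | a/b 3 | a/b 4 | a/b 10 |
|---|---|---|---|---|
| 28 Gy, <0.03 cc | 1.491 | 1.434 | 1.389 | 1.239 |
| 22 Gy, <0.35 cc | 1.458 | 1.396 | 1.349 | 1.204 |
| 15.6 Gy, <1.2 cc | 1.406 | 1.340 | 1.292 | 1.158 |

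Over alpha/beta 2-4 the excess is 29-49% across the three rows; at 10 it is 16-24%.

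**3-fraction totals with the same BED as the row in 5.** Solving for D gives D = 1.5 × (−a/b + √((a/b)² + 4 × (a/b) × BED/3)). Over alpha/beta 2-4:
- 28 Gy row: 22.4-23.0 Gy
- 22 Gy row: 17.8-18.3 Gy
- 15.6 Gy row: 12.8-13.2 Gy
- cauda equina 32 Gy row: 25.6-26.2 Gy
- cauda equina 30 Gy row: 24.0-24.6 Gy

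**How far the rows restrict a vertebral plan.**
- The 28 Gy cord maximum is above the full 27 Gy prescription. BED of 27 Gy in 3 is 148.5 at alpha/beta 2 and 87.75 at 4, against 106.4 and 67.2 for 28 Gy in 5. That is 40% and 31% higher, yet the row is met.
- The other two cord rows do restrict: 22/27 = 81% and 15.6/27 = 58% of a 27 Gy prescription. They are the working limits, and they are 29-46% looser.
- For the cauda equina, 110% of 27 Gy is 29.7 Gy, so both rows restrict little. The full 27 Gy in 3 has BED 5-10% above the 32 Gy row (2% below at alpha/beta 10) and 17-24% above the 30 Gy row (7% at 10).
- At a 30 Gy prescription, 110% is 33 Gy and both cauda equina rows can bind.

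**Opposite assumption.** If the totals were for 3 fractions, 28 Gy in 5 would have 0.671-0.720 of the intended BED. That is 28-33% tighter than needed for 5-fraction plans, with vertebral plans limited as intended.

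**The case against.** The strongest objection is that the fraction basis is not in the documents. Table 1 is said to be based on another trial's limits, whose fraction number is not given. Of the cord rows as printed, only the 15.6 Gy row carries a citation, to a review; the cauda equina rows cite a task-group report. No cord or cauda equina row cites RTOG 0813, the one source that the protocol itself ties to this schedule (section 2.3: "50 Gy in 5 fractions is the starting dose and fractionation of RTOG 0813"). Section 2.4's claim that every organ gets 5 fractions is general rationale that 6.5.1 overrides for vertebrae.

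A reader might also infer a 5-fraction basis from the rows at 53, 55 and 57 Gy. Section 6.5 says: "The PTV may be covered by a lower isodose line than usually used in conventional radiotherapy planning, ranging from 60-100" (percent), so a 30 Gy plan could reach at most 30/0.60 = 50 Gy. That shows only that the table was not built around a 30 Gy plan; a higher-dose 3-fraction regimen could also hold such rows. This objection stands: a 5-fraction basis is a reasonable reading, supported by aim 1.2.2 and the RTOG 0813 rows, but not an established fact.

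Second, there are other safeguards: a lower vertebral total, priority of normal tissue over coverage, no hot spots where the PTV overlaps an organ at risk, dose above 110% confined to the PTV, and exclusion of cord compression with deficit and of overlapping re-irradiation. The cord is also contoured as the bony canal, so true cord dose should be lower than recorded. These reduce the practical effect by an amount the documents do not allow one to estimate. None adjusts for the number of fractions.

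Third, using the 28 Gy row alone (39-49%) would put the weight on the least restrictive cord limit. The range across all three rows is the fair statement.

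**Conclusion.** The point holds as a defect in a stated rule. Binding limits are chosen by location only, from a table with no fraction number, in a protocol that prefers 3 fractions for one site and 5 for the rest. Whichever basis the table has, one of the two schedules is held to the wrong level.

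On the 5-fraction reading, with the linear-quadratic model and alpha/beta 2-4 Gy, the cord rows allow 29-49% more BED in vertebral plans (16-24% at alpha/beta 10). Confidence is medium, because the basis of the cord and cauda equina rows is inferred.

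Two stronger readings are not supported. One is that vertebral patients will receive that much more cord dose, or face that much more myelitis. The figures describe what a compliant plan may reach, a BED percentage is not a complication rate, and the documents give no number of vertebral patients. The other is that the safety monitoring is compromised: the event count, stopping boundary and power are unaffected.

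**What to change.** In section 6.6.1:

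1. Confirm the fraction basis of Table 1 against its source and state it in the table. It should not be labelled as 5-fraction without that check.
2. If the basis is 5 fractions, add 3-fraction limits for spinal cord and cauda equina, and for other organs near the spine where the source gives them. The matching values above show the likely direction and size; the limits themselves should come from the source, not from this calculation.
3. Reword the selection sentence so that limits depend on both lesion location and number of fractions.

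The cost is one label, a short extra table and one reworded sentence, with no added visits or patients. The downside is that some vertebral plans will lose target coverage beside the cord or cauda equina, which agrees with the priority that sections 6.5 and 6.5.1 already give to normal tissue.

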6.6.2 Critical Structure contouring

In order to verify each of these limits, the organs must be contoured such that appropriate volume histograms can be generated. The specific critical structures to be contoured and assessed by DVH for each case will be determined by the treating radiation oncologist. Instructions for the contouring of these organs are as follows:

Spinal Cord

The spinal cord will be contoured based on the bony limits of the spinal canal. The spinal cord should be contoured starting at least 5 cm above the superior extent of the PTV and continuing on every CT slice to at least 5 below the inferior extent of the PTV.

Cauda Equina

Starting at the conus (end of spinal cord, typically around L1 or L2) include the entire spinal canal into the sacrum to the filum.

Sacral Plexus

Include the nerve roots from L5 to S3 on each side from the neuroforamina to the coalescing of the nerves at the obturator internus muscle.

Esophagus

The esophagus will be contoured using mediastinal windowing on CT to correspond to the mucosal, submucosa, and all muscular layers out to the fatty adventitia. The esophagus should be contoured starting at least 5 cm above the superior extent of the PTV and continuing on every CT slice to at least 5 cm below the inferior extent of the PTV.

Brachial Plexus

The defined ipsilateral brachial plexus originates from the spinal nerves exiting the neuroforamina on the involved side from around C5 to T2. However, for the purposes of this protocol, only the major trunks of the brachial plexus will be contoured using the subclavian and axillary vessels as a surrogate for identifying the location of the brachial plexus. This neurovascular complex will be contoured starting proximally at the bifurcation of the brachiocephalic trunk into the jugular/subclavian veins (or carotid/subclavian arteries) and following along the route of the subclavian vein to the axillary vein ending after the neurovascular structures cross the second rib. If the PTV of all metastases is more than 5 cm away from the brachial plexus, this structure need not be contoured.

Heart

The heart will be contoured along with the pericardial sac. The superior aspect (or base) for purposes of contouring will begin at the level of the inferior aspect of the aortic arch (aortopulmonary window) and extend inferiorly to the apex of the heart.

Trachea and Proximal Bronchial Tree

The trachea and proximal bronchial tree will be contoured as two separate structures using mediastinal windows on CT to correspond to the mucosal, submucosa and cartilage rings and airway channels associated with these structures. For this purpose, the trachea will be divided into two sections: the proximal trachea and the distal 2 cm of trachea. The proximal trachea will be contoured as one structure, and the distal 2 cm of trachea will be included in the structure identified as proximal bronchial tree.

- Proximal Trachea

Contouring of the proximal trachea should begin at least 5 cm superior to the extent of the PTV for lung metastases or 5 cm superior to the carina (whichever is more superior) and continue inferiorly to the superior aspect of the proximal bronchial tree.

- Proximal Bronchial Tree

The proximal bronchial tree will include the most inferior 2 cm of distal trachea and the proximal airways on both sides as indicated in Figure 6-1. The following airways will be included according to standard anatomic relationships: the distal 2 cm of trachea, the carina, the right and left mainstem bronchi, the right and left upper lobe bronchi, the intermedium bronchus, the right middle lobe bronchus, the lingular bronchus, and the right and left lower lobe bronchi. Contouring of the lobar bronchi will end immediately at the site of a segmental bifurcation. If there are parts of the proximal bronchial tree that are within

GTV, they should be contoured separately, as “proximal bronchial tree GTV”, not as part of the “proximal bronchial tree”.

Whole Lung

Both the right and left lungs should be contoured as one structure. Contouring should be carried out using pulmonary windows. All inflated and collapsed lung should be contoured; however, gross tumor (GTV) and trachea/ipsilateral bronchus as defined above should not be included in this structure.

Skin

The skin will be defined as the outer 0.5 cm of the body surface. As such it is a rind of uniform thickness (0.5 cm) which envelopes the entire body in the axial planes. The cranial and caudal surface of the superior and inferior limits of the planning CT should not be contoured as skin unless skin is actually present in these locations (e.g., the scalp on the top of the head).

Great Vessels

The great vessels (aorta and vena cava, not the pulmonary artery or vein) will be contoured using mediastinal windowing on CT to correspond to the vascular wall and all muscular layers out to the fatty adventitia. The great vessel should be contoured starting at least 10 cm above the superior extent of the PTV and continuing on every CT slice to at least 10 cm below the inferior extent of the PTV. For right sided tumors, the vena cava will be contoured, and for left sided tumors, the aorta will be contoured.

Non-adjacent Wall of a Structure

For the esophagus, trachea and proximal bronchial tree, and great vessels, the nonadjacent wall corresponds to the half circumference of the tubular structure not immediately touching the GTV or PTV, These contours would start and stop superiorly and inferiorly just as with the named structure. The half lumen of the structure should be included in this contour.

Stomach

The entire stomach and its contents should be contoured as a single structure as a continuation of the esophagus and ending at the first part of the duodenum.

Duodenum

The wall and contents of the 1st, 2nd, and 3rd parts of the duodenum will be contoured as one structure beginning where the stomach ends and finishing as the superior mesenteric artery crosses over the third part of the duodenum.

Jejunum/Ileum

As a conglomerate of bowel loops within the abdomen distinguished from stomach, duodenum, and colon/rectum.

Bowel (Large/Small)

From the ileocecal area to include the ascending, transverse, descending and sigmoid colon as one structure.

Rectum

The entire rectum with contents from the peritoneal reflection of the sigmoid to the anus.

Bladder

This organ will be contoured as bladder wall exclusive of urinary contents

Kidney (renal cortex)

Both the right and left kidney, excluding renal pelvis/collecting system, should be contoured in their entirety (the renal cortex)

Liver

The entire liver minus the GTV targets.

Bile ducts

May use the portal vein from its juncture with the splenic vein to its right and left bifurcation in the liver as a surrogate to identify the bile ducts.

Femoral Heads

The ball of the head and socket joint.

Rib

Ribs within 5 cm of the PTV should be contoured by outlining the bone and marrow. Typically, several portions of adjacent ribs will be contoured as one structure. Adjacent ribs, however, should not be contoured in a contiguous fashion (i.e., do not include the inter-costal space as part of the ribs).

Other Structures

The constraints tables above contain other structures. These are required if the structure is within 5 cm of the PTV.

